# 11.3 Sample Size Considerations

The study will accrue a total of 60 randomized subjects (n=20 for the placebo arm A and n=40 for the LACTIN-V arm B). The accrual for this study is expected to be completed within 75 weeks (18 months) with projected accrual rate of 3 subjects per month. Each subject will be followed up for 64 days.

The primary endpoint upon which the sample size calculation was based is the proportion of subjects with a  $\geq 1 \text{ Log}_{10}$  decrease in at least 3 of 9 proinflammatory cytokines in CVL specimens on the Day 36 Visit, i.e. at the completion of the LACTIN-V/Placebo dosing phase. The proportion of women with decreased inflammation will be compared between the two study arms. This endpoint is adapted from the CAPRISA 004 study which demonstrated that women with the highest levels of at least 3 of 9 proinflammatory cytokines in CVL specimens had an increased risk of HIV acquisition. Our adaptation of the CAPRISA 004 analysis is that we will define "decreased inflammation" as a  $\geq 1 \text{ Log}_{10}$ decrease in the concentration of at least 3 of the same 9 proinflammatory cytokines. Based on our prior data, we assume that no more than 10% of placebo-treated women will achieve a decrease in  $\geq 3$  of the 9 proinflammatory genital tract cytokines. Moreover, we hypothesize that at least half of the participants in the treatment arm will achieve a decrease  $\geq 1 \log_{10}$  in  $\geq 3$  of the 9 proinflammatory genital tract cytokines. With the targeted sample size of 60 randomized women (1/3 in placebo arm & 2/3 in the LACTIN-V arm; there will be more than 88% power to detect a 40% absolute difference (10% vs. 50%) in the proportion of women with decreased inflammation between the two treatment arms. This power calculation was based on simulation study using 10,000 Monte Carlo samples and two-sided Fisher's exact test with type 1 error rate of 5%.

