#### 5.3 Treatment Assignment Procedures

#### 5.3.1 Randomization Procedures

Women will be randomized at the Randomization Visit 3 (Day 8) upon completion of the initial standardized antibiotic treatment with 2 x 400 mg daily over 7 days of oral metronidazole.

Women will be randomly assigned to receive LACTIN-V at  $2 \times 10^9$  cfu/dose or placebo in a 2:1 ratio. Enrolment will be continued until 60 women are randomized.

The list of randomized treatment assignments will be prepared by a statistician not involved with the study, and provided to the pharmacy, who will label the applicator pouches and cartons. Each carton will contain 11 study treatment applicators and be sequentially numbered according to the randomization scheme in a 2:1 (LACTIN-V to placebo) ratio.

Disenrolled participants before randomization will be replaced until 60 women are randomized into the study. Once randomized, participants will not be disenrolled.

Participants who test HIV-positive after randomization, will discontinue study product, but continue follow-up and attend all remaining study visits to monitor for adverse events. HIV-specific care, including the provision of antiretroviral treatment and ongoing management will be provided by the FRESH Study.

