#### 5.3.4 Handling of Withdrawals

Disenrolled participants before randomization will be replaced until 60 women are randomized into the study. Once randomized, participants will not be disenrolled. All randomized participants who are discontinued from receiving further study product will continue to be followed through the Final Visit 19.

If withdrawal of consent or study product discontinuation occurs after study treatment is initiated, the participant will be asked to continue scheduled study procedures including safety evaluations, if possible, and be given appropriate care under medical supervision if symptoms of any AEs related to participation in the study are continuing. The participant will be followed until the AE is resolved or until the participant's condition becomes stable.

Pregnant women will discontinue study product and continue to be followed through the Final Visit 19 in Week 9. All samples will be collected except those directly collected at the cervix.

Participants who withdraw their consent for further participation in the study after their study treatment ends or discontinue study product early will be reminded of the importance of continuing in the study for safety evaluations. Participants will be encouraged to complete the Early Termination evaluations described in section 7.9 if they choose not to complete the remaining study visits.

Participants who enrol in the study but do not return for study visits after a minimum of three attempts to contact them over a 2-week period will be considered lost to follow-up.

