# 7.0 STUDY SCHEDULE

# 7.1 Enrolment Visit 1

The purpose of the Enrolment Visit 1 is to complete the informed consent process and identify participants who satisfy all eligibility criteria.

Women who are part of the FRESH study cohort can be recruited for the LACTIN-V study. Potentially eligible participants will be approached during the regular Week 5 FRESH Study Visit that includes a pelvic exam and mucosal sampling. Women will receive information about the opportunity to co-enrol in LACTIN-V. Should they be interested in participating in the LACTIN-V study, they will be told that some of the test results routinely collected at the Week 5 FRESH Study Visit will be used to assess their eligibility for LACTIN-V, and that they would be contacted should they meet the following eligibility criteria:

- 1. non-*Lactobacillus* dominated vaginal microbiota as determined by Nugent score 4-10 on vaginal Gram stain
- 2. negative STI testing results
- 3. on stable long acting injectable contraception, either on Depot Medroxyprogesterone Acetate (DepoProvera) or norethisterone enanthate (NetEn), or an IUD or implant for at least 3 months.

Interested women who meet these eligibility criteria for LACTIN-V will be contacted after review of the laboratory results, usually within 7-10 days. In accordance with their menstrual cycle and expected onset of the next menses, they will be invited and scheduled for a LACTIN-V Enrolment Visit that will take place on a date at least 12 days before the next expected menses, and no later than 30 days after the Week 5 FRESH Study Visit.

Eligible women who agree to be enrolled in LACTIN-V will be asked to sign the informed consent form available in English and isiZulu that will describe the purpose of the study, the procedures to be followed, and the risks and benefits of the study, and will include a separate section for consent to store samples for future use. An Assessment of Understanding form, available in English and isiZulu, will be completed to ensure that study participants retained the most important aspects of the provided information. A copy of the consent form will be given to the participant and this fact will be documented in the medical record.

Participants will be asked to provide contact information (i.e., address, email address, home/cell phone number, emergency contact), which will be recorded on the appropriate contact form, which will be kept away from other study forms in a locked cabinet.

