# 11.2 Study Objectives and Outcome Measures

As described in section 3.2 and 3.3, the primary study objectives are to compare LACTIN-V with placebo following a 7-day treatment course with Metronidazole with respect to safety and impact on the vaginal microbiome, specifically *lactobacillus* growth and decrease in pro-inflammatory cytokines and HIV target cells.

In Objective 1, the outcomes of interest will be:

(1) a decrease in genital tract inflammation from baseline (the FRESH Study Visit before enrollment) to Day 36 Follow-Up Visit, as defined by a  $\geq$ 1 Log10 decrease in the concentration of cytokines that have been associated with an increased risk for HIV infection., and

(2) the change in the concentration of cytokines at the Final Visit on Day 64 (4 weeks after dosing phase completed) compared to baseline, number of endocervical CD4+ HIV target cells at Day 36 Follow-Up and Day 64 Final Visits compared to baseline, and in vitro anti-HIV activity of cervicovaginal lavage at Day 36 Follow-Up and Day 64 Final Visits. We will compare each outcome by study arm.

In Objective 2, the outcomes of interest will be:

(1) the presence of *Lactobacillus*-dominant vaginal microbial cervicotypes at the Day 36 Follow-Up Visit, and following the post-dosing phase at the Day 64 Final Visit in the LACTIN-V arm; and

(2) the comparison of *L. crispatus* vs. *L. iners* prevalence between treatment groups, quantity of vaginal *L. crispatus*, presence of the specific CTV-05 *L. crispatus* strain, persistence of colonization after stopping therapy, effect of sex and/or vaginal hygiene practices on colonization by lactobacilli, and stability of vaginal microbial communities over time in the treatment vs. placebo arms.

In Objective 3, the outcomes of interest will be:

- (1) the proportion of treatment related adverse events study arm, in particular Grade 3 AEs; and
- (2) the proportion of participants finding the product acceptable and are willing to use it Page 64 of 124

should it become commercially available, as measured in a standardized acceptability questionnaire.

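### Is the power of more than 88% in section 11.3 undermined by the lack of a dropout allowance, or by accrual figures that do not agree?

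*Combined protocol and SAP*

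**What the plan says.** Section 11.3 plans 20 women on placebo and 40 on LACTIN-V. The endpoint is a fall of at least 1 log10 in at least 3 of 9 proinflammatory cytokines in lavage fluid at Day 36. The response rates are set as bounds: no more than 10% on placebo and at least half on LACTIN-V. The power sentence opens "With the targeted sample size of 60 randomized women" and states that "there will be more than 88% power to detect a 40% absolute difference (10% vs. 50" percent), from 10,000 simulated trials with a two-sided Fisher's exact test at 5%.

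Section 11.2 defines the outcome as "a decrease in genital tract inflammation from baseline (the FRESH Study Visit before enrollment) to Day 36 Follow-Up Visit", so each woman needs two cytokine results. Section 7.1 describes the "regular Week 5 FRESH Study Visit that includes a pelvic exam and mucosal sampling", which supplies the first.

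On retention, section 5.3.1 says "Disenrolled participants before randomization will be replaced until 60 women are randomized into the study". Section 5.3.4 says that women who cannot be reached after at least three attempts "over a 2-week period will be considered lost to follow-up", and that randomised women "discontinued from receiving further study product will continue to be followed through the Final Visit 19".

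On accrual, section 11.3 expects enrolment to be "completed within 75 weeks (18 months) with projected accrual rate of 3 subjects per month". The Protocol Summary gives 65 weeks to complete enrolment and a study duration of 90 weeks.

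**The concern.** The power is claimed for everyone randomised, but the endpoint can be scored only in women with results at both time points. Replacement ends at randomisation and loss to follow-up is foreseen. No eligibility criterion requires a usable baseline cytokine result, section 11.3 makes no allowance for women who cannot be scored, and section 11.5 gives no rule for missing cytokine results. With arms of 20 and 40, a few lost samples might pull the real power well below the headline. If so, the trial could be too small for its primary question, and a null result would be hard to read.

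The accrual sentence adds to the doubt. Its three figures cannot all be right, and the Protocol Summary gives a fourth. If the study were to stop on a calendar date, fewer than 60 women could be randomised and the power would fall for that reason too.

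**Working it through.** **Inputs.** From section 11.3: 20 and 40 women, 10% versus 50%, two-sided Fisher's exact test at 5%, accrual of 3 per month over 75 weeks (18 months), 64 days of follow-up. From the Protocol Summary: 65 weeks of enrolment, 90 weeks in all. Loss rates are assumptions, because the documents give none for this trial.

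**1. The plan's own figure.** Let R be the set of outcomes (a responders of 20, b responders of 40) with Fisher p ≤ 0.05. Then

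power = Σ over R of Bin(a; 20, 0.10) × Bin(b; 40, 0.50) = 0.891.

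The plan's "more than 88%" is reproduced.

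**2. Complete cases only, loss at random.** With loss rate d, the numbers evaluable are Bin(20, 1−d) and Bin(40, 1−d). Power is averaged over them.

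| Assumed loss | Average power |
|---|---|
| 0% | 0.891 |
| 3% | 0.883 |
| 5% | 0.874 |
| 10% | 0.845 |
| 15% | 0.813 |

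The average crosses 0.88 at 3.7% loss (0.037 × 60 ≈ 2 women) and 0.80 at about 17.2% (0.172 × 60 ≈ 10 women).

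These are averages. Exact power does not fall smoothly with sample size: 18/40 evaluable gives 0.878 and 19/37 gives 0.859, but 19/36 and 20/35 both give 0.882. Five women can therefore be missing with power still above 88%, while some splits with two missing fall just short of it.

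**3. Missing counted as non-response.** The arms stay at 20 and 40, with rates 0.10 × (1−d) and 0.50 × (1−d). Power is 0.864 at 5% loss, 0.833 at 10% and 0.798 at 15%.

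**4. Comparison with the other inputs.** The placebo rate is stated as an upper bound. At 8% instead of 10%, power with all 60 evaluable is 0.933. With 10% proportional loss (18/36) it is 0.898. Two points on the placebo rate raise power by 0.933 − 0.891 = 0.042. Five per cent loss lowers it by 0.891 − 0.874 = 0.017.

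**5. Accrual.** One month is about 4.348 weeks.

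- 18 months × 3 = 54 women, and 18 × 4.348 = 78.3 weeks, not 75.
- 75 weeks = 17.25 months, and 17.25 × 3 ≈ 52 women.
- 65 weeks = 14.95 months, and 14.95 × 3 ≈ 45 women.
- 60 / 3 = 20 months = 87.0 weeks. Adding 64/7 = 9.1 weeks of follow-up gives 96.1 weeks, against 90 stated.
- If "3" is 60/18 = 3.33 rounded down, 60 women in 18 months is right and ends at 78.3 + 9.1 = 87.4 weeks, within the 90. The 75- and 65-week figures still conflict with it.

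**The case for a change.** The strongest case for a change is that the power figure cannot be tied to any planned analysis. The abbreviation list defines complete case, last observation carried forward, modified intention-to-treat and per protocol, yet section 11 uses none of them. The only evaluability figure in the documents comes from the sponsor's Phase 2b trial in section 2.4, with 88% and 84% evaluable. Applied here (about 35 and 17 women), it gives power of about 0.83 in that split, or 0.81 averaged over random loss. A sentence on missing results would cost nothing and would prevent a choice made after unblinding.

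Part of this stands. No allowance is stated, no missing-data rule is written, and stating the condition would be good practice. But the Phase 2b figure is for a 12-week outcome in another trial, and even that leaves power above 80%. Here the endpoint falls four weeks after randomisation, in women who already attend the same clinic twice a week for FRESH and receive reminders (section 4.0). Women who stop product stay in follow-up, Visit 11 has a window of Days 33 to 43 (section 7.5), and lavage is also taken at discontinuation or early termination (section 7.8), although no text says that such a sample counts as Day 36. Baseline loss should be small too, because section 2.5 describes FRESH as collecting lavage at its scheduled mucosal sampling.

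The accrual contradiction cannot be argued away. It is an error of arithmetic in a forecast.

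**Conclusion.** No change to the plan follows. The power statement is correct on the basis it gives: 0.891 with all 60 women evaluable. The unstated condition costs about 2 points at 5% loss and about 8 at 15% (complete case, loss at random and equal in both arms). Power stays above 80% up to about 17% loss, or about 14.7% if missing counts as non-response. These loss rates are assumed. The effect of modest loss is smaller than that of a two-point shift in the placebo rate. Writing in an allowance would leave the sample size and Fisher's test as they are, and the analysts can settle the handling of a few missing results before unblinding.

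The accrual figures do not agree, and exactly 3 per month would overrun the 90 weeks by about 6 (96.1 − 90). This is a clerical slip. Sections 4.0, 5.0 and 5.3.1 all continue enrolment until 60 women are randomised, so no power figure or analysis depends on the forecast. It can be tidied whenever the document is next revised.

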## 11.4 Safety Analysis

This study will be monitored for safety and to determine if any of the safety halting rules described in detail in Section 9.5 are met (one or more treatment-related SAE, two or more treatment-related vaginal ulceration, two or more treatment-related severe Grade 3 systemic adverse events). Thus, all patients will be evaluated for toxicity. The DSMB will review interim analyses comparing product-related AEs between the two treatment arms will be performed after half of the 60 participants complete the Follow-Up Study Visit 11, and then annually. Reports of these analyses will be sent to the Principal Investigator or Senior Investigators at the participating institutions.

The table below gives the probability of observing at least one incidence of AE together with the corresponding true AE rate for a total of 60 participants.

True AE rate:	0.5%	1%	2%	5%
P [AE>1]:	0.26	0.45	0.70	0.95

For example, the probability of observing at least one incidence of AE with true rate of 5% is 0.95.

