## 4.0 STUDY DESIGN

This is a Phase 2 randomized double-blind placebo-controlled trial to assess the impact of the live biotherapeutic product LACTIN-V containing *Lactobacillus crispatus* CTV-05 on the vaginal microbiome of young women in South Africa at high risk of HIV acquisition.

The study will also assess the safety of LACTIN-V by comparing the incidence of AEs between women randomized to LACTIN-V or placebo.

We will conduct a randomized, placebo-controlled trial of LACTIN-V in a cohort of young South African women with a non-*Lactobacillus* dominant microbiota, who are sexually experienced, age 18 to 23 years. Enrolment will be continued until 60 women will be randomized into the study.

Eligible women will be treated with oral metronidazole 400 mg twice daily for seven days and will then be randomized 2:1 to LACTIN-V vs. placebo.

Within 8-48 hours of taking the final metronidazole dose, women will receive the study product for five consecutive days, followed by a twice weekly dose for three additional weeks.

After enrolment and metronidazole treatment, women will be followed throughout the 4 weeks of dosing and the 4 weeks of post-dosing phase for a total of 10 weeks (until approximately Day 64).

The primary outcome (**Objective 1**) focuses on the ability of the *L. crispatus* CTV-05 to acutely decrease genital tract inflammation (as a marker of HIV susceptibility). This will be assessed by collecting cervicovaginal fluid and endocervical immune cells at randomization (Day 8), after 4 weeks of treatment with the LACTIN-V vs. placebo (Day 36), and after 4 weeks of post-dosing phase (Day 64).

Direct anti-HIV activity will be assessed with *in vitro* HIV infection assays using vaginal fluid samples from randomization and after treatment: Randomization Visit (Day 8), Follow-up Visit (Day 36), and Final Visit at Day 64.

A secondary outcome (**Objective 2**) is to assess the ability of the *L. crispatus* CTV-05 to establish durable vaginal colonization as with the potential as a self-sustaining prevention strategy. This will be assessed by characterization of the vaginal microbiome at the baseline FRESH Study Visit, and the end of treatment (Day 36) and at the Final Visit (Day 64), after 4 additional weeks during the post-treatment phase.

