#### 5.3.2 Blinding Procedures

At the time of randomization, the site pharmacist will select the next available box of study product applicators in sequential order and will distribute to masked study personnel with no labels that identify the product or applicators as LACTIN-V or placebo. No masking procedures are required for the metronidazole treatment.

The participants, study personnel who perform study assessments, data entry personnel at the sites, and laboratory personnel performing study assays will be blinded to treatment assignment. The Data and Safety Monitoring Board (DSMB) may receive data in aggregate and presented by treatment group, but without the treatment group identified. The DSMB may be unmasked to individual study treatment assignments, as needed, to adequately assess safety issues. Refer to the MOP for unmasking procedures, including emergency unblinding procedures.

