# 9.2 Methods and Timing for Assessing, Recording, and Analyzing Safety Parameters

#### 9.2.1 Adverse Events

ICH (International Conference on Harmonisation) E6 defines an AE as any untoward medical occurrence in a patient or clinical investigation subject administered a pharmaceutical product regardless of its causal relationship to the study treatment. An AE can therefore be any unfavorable and unintended sign (including an abnormal laboratory finding), symptom, or disease temporally associated with the use of medicinal (investigational) product. The occurrence of an AE may come to the attention of study personnel during study visits and interviews of a study participant presenting for medical care, or upon review by a study monitor.

All AEs including local and systemic reactions not meeting the criteria for "serious adverse events" should be captured on the appropriate CRF and will include:

- Vaginal bleeding other than menstruation
- Abnormal vaginal discharge
- Abnormal vaginal odor
- Genital itching
- Genital burning
- External genitalirritation
- External genital swelling
- Nausea
- Vomiting
- Abdominal pain/cramps
- Diarrhea
- Constipation
- Genital rash
- Pain/burning with urination
- Frequent urination
- Blood in urine
- Headache

Information to be collected includes event description, time of onset, clinician's assessment of severity, relationship to study product (assessed only by those with the training and authority to make a diagnosis), and time of resolution/stabilization of the event. All AEs occurring while on study must be documented appropriately regardless of relationship. All AEs will be followed to adequate resolution.

Any medical condition that is present at the time that the participant is screened should be considered as baseline and not reported as an AE. However, if it deteriorates at any time during the study, it should be recorded as an AE. All AEs must be graded for severity and relationship to study product. The FDA defines an AE as any untoward medical occurrence associated with the use of a drug in humans, whether or not considered drug related.

Severity of Event: All AEs will be assessed by the clinician using a protocol-defined grading system. For events not included in the protocol-defined grading system, the following guidelines will be used to quantify intensity.

- Mild (Grade 1): Events require minimal or no treatment and do not interfere with the participant's dailyactivities.

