- Moderate (Grade 2): Events result in a low level of inconvenience or concern with the therapeutic measures. Moderate events may cause some interference with functioning.
- Severe (Grade 3): Events interrupt a participant's usual daily activity and may require systemic drug therapy or other treatment. Severe events are usually incapacitating.
- Life-threatening (Grade 4): Life-threatening consequences; urgent intervention indicated.

Changes in the severity of an AE should be documented to allow an assessment of the duration of the event at each level of intensity to be performed. AEs characterized as intermittent require documentation of onset and duration of each episode.

Relationship to Study Products: The clinician's assessment of an AE's relationship to test article is part of the documentation process, but it is not a factor in determining what is or is not reported in the study. If there is any doubt as to whether a clinical observation is an AE, the event should be reported. All AEs must have their relationship to study product assessed using the terms: related or not related. In a clinical trial, the study product must always be suspect. To help assess, the following guidelines are used.

- Related: There is a reasonable possibility that the study product caused the AE. Reasonable possibility means that there is evidence to suggest a causal relationship between the study product and the AE.
- Not Related: There is not a reasonable possibility that the administration of the study product caused the event.

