#### 9.2.2 Serious Adverse Events

An AE or SAE reaction is considered "serious" if, in the view of either the investigator or sponsor, it results in any of the following outcomes:

- Death
- A life-threatening adverse event\*

- Inpatient hospitalization or prolongation of existing hospitalization
- A persistent or significant incapacity or substantial disruption of the ability to conduct normal life functions
- A congenital anomaly/birth defect.
- Important medical events that may not result in death, be life-threatening, or require hospitalizations may be considered serious when, based upon appropriate medical judgment they may jeopardize the participant and may require medical or surgical intervention to prevent one of the outcomes listed in this definition. Examples of such medical events include allergic bronchospasm requiring intensive treatment in an emergency room or at home, blood dyscrasias or convulsions that do not result in inpatient hospitalization, or the development of drug dependency or drugabuse.
- \*Life-threatening adverse event. An AE is considered "life-threatening" if, in the view of either the investigator or sponsor, its occurrence places the participant at immediate risk of death. It does not include an AE that, had it occurred in a more severe form, might have caused death.

All SAEs will be:

- Recorded on the appropriate SAE form and CRF
- Followed through resolution by a study physician
- Reviewed and evaluated by the study chairs, relevant IRBs, and the DSMB
- 9.2.3 Procedures to be followed in the Event of Abnormal Laboratory Test Values or Abnormal Clinical Findings

The site principal investigator or appropriate sub-investigator is responsible for reporting all AE/SAEs that are observed or reported during the study, regardless of their relationship to study product. AE/SAEs, abnormal laboratory values, or abnormal clinical findings will be documented, reported, and followed appropriately.

For grading abnormal gynaecological events, refer to Appendix B, Division of AIDS Table for Grading the Severity of Adult and Pediatric Adverse Events, December 2004; Addendum 1: Female Genital Grading Table for Use in Microbicide Studies, November 2007.

For grading abnormal laboratory and clinical events, refer to Appendix C, DAIDS Toxicity Table for Grading the Severity of Adult and Pediatric Adverse Events, Version 2.1 July 2017.

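### Section 11.4 sends reports of mid-trial between-arm AE comparisons to investigators in a double-blind trial; by-arm reports should stay with the DSMB

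*Combined protocol and SAP*

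**What the plan says.** Section 4.0 sets the design: "This is a Phase 2 randomized double-blind placebo-controlled trial".

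Section 11.4 has the DSMB review safety data partway through: "interim analyses comparing product-related AEs between the two treatment arms will be performed after half of the 60 participants" complete Visit 11. It adds annual analyses after that. The next sentence names the recipients: "Reports of these analyses will be sent to the Principal Investigator or Senior Investigators at the participating institutions".

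Section 5.3.2 blinds participants, staff carrying out assessments, data-entry staff and laboratory staff. It says the DSMB may receive aggregate data "presented by treatment group, but without the treatment group identified", with a route to more if needed: "The DSMB may be unmasked to individual study treatment assignments, as needed, to adequately assess safety issues". It sets no rule for what investigators may receive.

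Section 9.6 is narrower than 11.4. It has the DSMB tell UKZN, UCSF and the Ragon Institute what it found and does not mention by-arm tables. Section 15.4 lets the sponsor generate interim statistical reports at its discretion and adds no restriction on content or recipients.

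On AE judgements, section 9.2.1 makes the call binary: "All AEs must have their relationship to study product assessed using the terms: related or not related". The clinician makes the first assessment. Section 9.2.3 adds: "The site principal investigator or appropriate sub-investigator is responsible for reporting all AE/SAEs that are observed or reported during the study". Section 15.1 has the site PI or a designee review AEs, which must be assessed for severity and causality.

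**The concern.** The analyses named in the recipient sentence are the between-arm comparisons described immediately before it. Followed literally, the plan gives investigators by-arm safety results during the trial under no stated mask, which is looser than the format described for the DSMB itself.

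Relatedness is a judgement, and much rests on it. Product-related AEs by arm are the safety outcome for Objective 3 (3.4.1 and 11.2). The first three halting rules in 9.5 depend on an event being treatment-related, and under the first a single treatment-related SAE is enough. If the site PI receives the report, later causality reviews could be made knowing which event types had clustered in one arm.

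**Working it through.** The plan gives no figure on this point. Two quantities show its size: how many AE judgements are still to come when the report is issued, and whether coded groups would protect the blind.

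**1. Women with AE judgements still to come**

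Inputs:
- 60 women; the look follows the 30th completed Visit 11 (11.4).
- Randomisation is Day 8, Visit 11 is Day 36 and the Final Visit is Day 64. Visit 11 therefore falls 28 days (4 weeks) after randomisation, and follow-up ends at 56 days (8 weeks).
- The documents give three accrual figures: 65 weeks (Protocol Summary), 75 weeks (11.3) and 3 per month (11.3). The last implies 20 months × 52/12 = 86.7 weeks. Weekly rates r are 60/65 = 0.923, 60/75 = 0.800 and 3/(52/12) = 0.692.
- Assumptions: uniform accrual, and a lag of L weeks between the 30th Visit 11 and the report. The documents state no lag.

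Women still exposed are those not yet randomised plus those randomised less than 8 weeks before the report:

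(30 − (4 + L)r) + 8r = 30 + (4 − L)r

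This form holds while accrual is still open, as it is in every case below.

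| Accrual | L = 0 | L = 4 | L = 8 |
|---|---|---|---|
| 65 weeks | 26.3 + 7.4 = 33.7 | 22.6 + 7.4 = 30.0 | 26.3 |
| 75 weeks | 26.8 + 6.4 = 33.2 | 23.6 + 6.4 = 30.0 | 26.8 |
| 3 per month | 27.2 + 5.5 = 32.8 | 24.5 + 5.5 = 30.0 | 27.2 |

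That is 55 to 56% of 60 with no lag, 50% with 4 weeks and 44 to 45% with 8 weeks. If the Final Visit falls at the end of its window (Day 71, 9 weeks after randomisation), the no-lag figure is 30 + 5r, at most 30 + 5 × 0.923 = 34.6.

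**2. Would coded groups keep the arms hidden?**

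Allocation is 2:1, with 40 women on LACTIN-V and 20 on placebo. Suppose the report shows group sizes (the documents do not say) for the first 30 women. The randomisation method is not stated, so a range is given.

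- Simple randomisation: P(Bin(30, 2/3) > 15) = 0.957 that the larger group is LACTIN-V (tie 0.025, reversed 0.019).
- Unblocked list of 40 and 20, first 30 places (hypergeometric): 0.994 (tie 0.005, reversed 0.001).
- Permuted blocks of 3 or 6: exactly 20 to 10. Blocks of 9: three full blocks give 18 on LACTIN-V before the last 3 women. Blocks of 12: two full blocks give 16, and at most 4 of the next 6 are placebo, so at least 18. The probability is 1.00.

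Section 11.3 also labels placebo as arm A and LACTIN-V as arm B, so reusing those letters would identify the groups outright.

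**The case against.** The strongest reply is that this is loose wording and not a break in the blind.

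- Section 5.3.2 does not name the PI among those blinded, and an aggregate table reveals no woman's assignment. Both are true, so the conflict is inferred from the double-blind design and the PI's review role.
- The analyses are the ones the DSMB reviews, so a report of them might carry the same coded groups. But 5.3.2 is permissive and written for the DSMB only, and coding is weak under 2:1 allocation.
- There is one clinical site, so the plural institutions may be the three bodies in 9.6, and the report may mean only the DSMB's findings. The 11.4 sentence reads like two run together. The DSMB charter, not seen here, may also set reporting rules. This reading is possible, but the text says reports of the analyses and does not exclude the site PI.
- SAEs are also reviewed by the study chairs, IRBs, the DSMB and the medical monitor (9.2.2, 9.3.1). That protects the SAE trigger to some degree. It does not cover relatedness calls on non-serious events.
- The counts above measure remaining exposure, not bias, and any mid-trial look would leave women in follow-up. This stands: no change in relatedness calls has been estimated.

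**Conclusion.** The concern holds and should be fixed, with medium confidence. As written, 11.4 permits by-arm interim safety results to reach someone who reviews causality while roughly half the women still have AE judgements ahead: 33 to 34 of 60 with no reporting lag (up to about 34.6 with the widest final-visit window), and 26 to 27 with an assumed 8-week lag. These figures rest on uniform accrual and matter only if the site PI, or another causality reviewer, is a recipient.

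The consequence is limited. Because a woman's own arm stays unknown, the effect on the between-arm comparison has no clear direction, although the overall level of related calls could shift. AE analysis is mainly descriptive (11.5), though Fisher's exact test compares the rates. The laboratory cytokine endpoint is largely unaffected, and no sample-size or power figure changes.

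**What to change.** Replace the recipient sentence in 11.4 with:

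> By-arm interim reports, including any produced under 15.4, go only to the DSMB and to the coordinating-centre staff who prepare them, in the format set by 5.3.2. Until database lock, investigators receive the DSMB's recommendation and AE counts pooled over both arms, except where unmasking is needed under 5.3.2 or the MOP.

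The cost is small. The coordinating centre already has analysis and reporting (15.1), the DSMB already advises the institutions (9.6), and the existing unmasking route is kept. The staff who hold the code should be named, since no passage now does so; any by-arm report needs this anyway. The downside is that investigators wait until lock for by-arm safety data.

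As housekeeping, give one DSMB calendar in 9.6 and 11.4. Section 9.6 has one interim meeting and one after database lock; only 11.4 adds annual analyses.
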